8.1.2. Pharmacodynamics

LIPITOR, as well as some of its metabolites, are pharmacologically active in humans. The liver is the primary site of action and the principal site of cholesterol synthesis and

LDL clearance. Drug dosage, rather than systemic drug concentration, correlates better with LDL-C reduction.

8.1.3. **Pharmacokinetics**

Absorption: LIPITOR is rapidly absorbed after oral administration; maximum plasma concentrations occur within 1 to 2 hours. Extent of absorption increases in proportion to LIPITOR dose. The absolute bioavailability of atorvastatin (parent drug) is approximately 14% and the systemic availability of HMG-CoA reductase inhibitory activity is approximately 30%. The low systemic availability is attributed to presystemic clearance in gastrointestinal mucosa and/or hepatic first-pass metabolism. Although food decreases the rate and extent of drug absorption by approximately 25% and 9%, respectively, as assessed by Cmax and AUC, LDL-C reduction is similar whether LIPITOR is given with or without food.

8.1.4. **Contraindications**

Active Liver Disease which may include Unexplained Persistent Elevations of Hepatic Transaminase Levels

Hypersensitivity to any Component of this Medication

Pregnancy

Nursing Mothers

8.1.5. **Drug Interactions**

Drug Interactions Associated with Increased Risk of Myopathy/Rhabdomyolysis include the following.

Interacting Agents	Prescribing Recommendations
Cyclosporine	Atorvastatin is a substrate of the OATP1B1 transporter. Inhibitors of the OATP1B1 (e.g., cyclosporine) can significantly increase the bioavailability of atorvastatin. Concomitant administration of atorvastatin and cyclosporine is not permitted on the protocol.
Clarithromycin, itraconazole, HIV protease inhibitors	Caution when exceeding doses

(ritonavir plus saquinavir or lopinavir plus ritonavir)	> 20mg atorvastatin daily. The lowest dose necessary should be used.
Atorvastatin is metabolized by cytochrome P450 3A4. Concomitant administration of atorvastatin with inhibitors of cytochrome P450 3A4 can potentially lead to increased plasma atorvastatin concentrations.	Use of strong inhibitors of cytochrome P450 3A4 (erythromycin, clarithromycin, protease inhibitors, diltiazem, or itraconazole), with atorvastatin should be done with caution.
Grapefruit juice	: Contains one or more components that inhibit CYP 3A4 and can increase plasma concentrations of atorvastatin, especially with excessive grapefruit juice consumption (>1.2 liters per day).
Gemfibrozil	Due to an increased risk of myopathy/rhabdomyolysis when HMG-CoA reductase inhibitors are co-administered with gemfibrozil, concomitant administration of LIPITOR with gemfibrozil should be avoided
Digoxin	Digoxin concentrations are unaffected by atorvastatin doses of <80mg/day
Rifampin or other Inducers of Cytochrome P450 3A4:	Concomitant administration of LIPITOR with inducers of cytochrome P450 3A4 (e.g., efavirenz, rifampin) can lead to variable reductions in plasma concentrations of atorvastatin. Due to the dual interaction mechanism of rifampin, simultaneous co-administration of LIPITOR with rifampin is recommended, as delayed administration of LIPITOR after administration of rifampin has been associated with a significant reduction in atorvastatin plasma concentrations.

8.1.6. **Adverse Events:**

Skeletal Muscle

Rare cases of rhabdomyolysis with acute renal failure secondary to myoglobinuria have been reported with LIPITOR and with other drugs in this class. A history of renal impairment may be a risk factor for the development of rhabdomyolysis. Such patients merit closer monitoring for skeletal muscle effects. Atorvastatin, like other statins, occasionally causes myopathy, defined as muscle aches or muscle weakness in conjunction with increases in creatine phosphokinase (CPK) values >10 times ULN. The concomitant use of higher doses of atorvastatin with certain drugs such as cyclosporine and strong CYP3A4 inhibitors (e.g., clarithromycin, itraconazole, and HIV protease inhibitors) increases the risk of myopathy/rhabdomyolysis. Myopathy should be considered in any patient with diffuse myalgias, muscle tenderness or weakness, and/or marked elevation of CPK. Patients should be advised to report promptly unexplained muscle pain, tenderness, or weakness, particularly if accompanied by malaise or fever. LIPITOR therapy should be discontinued if markedly elevated CPK levels occur or myopathy is diagnosed or suspected.

Liver Dysfunction

Statins, like some other lipid-lowering therapies, have been associated with biochemical abnormalities of liver function. Persistent elevations (>3 times the upper limit of normal [ULN] occurring on 2 or more occasions) in serum transaminases occurred in 0.7% of patients who received LIPITOR in clinical trials. The incidence of these abnormalities was 0.2%, 0.2%, 0.6%, and 2.3% for 10, 20, 40, and 80 mg, respectively.

Endocrine Function

Statins interfere with cholesterol synthesis and theoretically might blunt adrenal and/or gonadal steroid production. Clinical studies have shown that LIPITOR does not reduce basal plasma cortisol concentration or impair adrenal reserve. The effects of statins on male fertility have not been studied in adequate numbers of patients. The effects, if any, on the pituitary-gonadal axis in premenopausal women are unknown. Caution should be exercised if a statin is administered concomitantly with drugs that may decrease the levels or activity of endogenous steroid hormones, such as ketoconazole, spironolactone, and cimetidine.

CNS Toxicity

Brain hemorrhage was seen in a female dog treated for 3 months at 120 mg/kg/day. Brain hemorrhage and optic nerve vacuolation were seen in another female dog that was sacrificed in moribund condition after 11 weeks of escalating doses up to 280 mg/kg/day. The 120 mg/kg dose resulted in a systemic exposure approximately 16 times the human plasma area-under-the-curve (AUC, 0-24 hours) based on the maximum human dose of 80 mg/day. A single tonic convulsion was seen in each of 2 male dogs (one treated at 10 mg/kg/day and one at 120 mg/kg/day) in a 2-year study. No CNS lesions have been observed in mice after chronic treatment for up to 2 years at doses up to 400 mg/kg/day or in rats at doses up to 100 mg/kg/day. These doses were 6 to 11 times (mouse) and 8 to 16 times (rat) the human AUC (0-24) based on the maximum recommended human dose of 80 mg/day.

Other adverse reactions reported in placebo-controlled studies include: *Body as a whole*: malaise, pyrexia; *Digestive system*: abdominal discomfort, eructation, flatulence, hepatitis, cholestasis; *Musculoskeletal system*: musculoskeletal pain, muscle fatigue, neck pain, joint swelling; *Metabolic and nutritional system*: transaminases increase, liver function test abnormal, blood alkaline phosphatase increase, creatine phosphokinase increase, hyperglycemia; *Nervous system*: nightmare; *Respiratory system*: epistaxis; *Skin and appendages*: urticaria; *Special senses*: vision blurred, tinnitus; *Urogenital system*: white blood cells urine positive.

8.2. How supplied and Storage/Handling

40 mg tablets: coded “PD 157” on one side and “40” on the other.

NDC 0071-0157-23 bottles of 90

NDC 0071-0157-73 bottles of 500

NDC 0071-0157-88 bottles of 2500

NDC 0071-0157-40 10 x 10 unit dose blisters

Stored at controlled room temperature 20 - 25°C (68 - 77°F).

8.3. Methods of procurement

The Medical College of Wisconsin & West Virginia University Hospitals Departments of Pharmacy will order Atorvastatin 40mg and receive drug specifically for this study. The CTRU (at WVU) and CTO (at MCW) will be billed for the cost of the drug which will be paid for by study funds. The drug will be dispensed per patient and labeled according to more stringent state or federal law. Drug accountability and inventory records will be created and maintained within the Investigational Drug Services.

9. Statistical Considerations:

The study is a single-arm phase II trial evaluating the safety and efficacy of atorvastatin for the prophylaxis of acute GVHD in patients with hematological malignancies undergoing HLA-matched HSCT. The primary objective of this study is to evaluate the cumulative incidence of grade II-IV acute GVHD by day +100 in patients receiving acute GVHD prophylaxis with atorvastatin, tacrolimus and methotrexate. The incidence of grade II-IV acute GVHD in patients undergoing MAC or RIC matched sibling allogeneic SCT, and receiving GVHD prophylaxis with tacrolimus and methotrexate is approximately 30-40%. The respective rates for patients undergoing RIC unrelated donor transplantation with ATG are 45-55% and without ATG 50-60%. The sibling and unrelated donor arms of this study will be analyzed separately, with aim for separate publications. At the time of publication the results of unrelated donor arm of the study will be retrospectively compared against patients undergoing unrelated transplantation at our center after conditioning with Flu/Bu2 or Flu/Bu4 and receiving GVHD prophylaxis with tacrolimus, MTX and ATG.

For this phase II study, we will use an open-label, minimax two-stage design as specified by Simon. We will consider the “experimental” acute GVHD prophylactic regimen of atorvastatin/tacrolimus/methotrexate to be no more effective than GVHD prophylaxis with tacrolimus/methotrexate alone for matched sibling allogeneic HCT, if the true probability of developing grade II-IV acute GVHD is more than 35% (p_0). We will also assume that the new prophylactic regimen is worthy of further study if the true probability of grade II-IV

acute GVHD is equal or less than 15% (p1). In statistical terms, we are testing the null hypothesis $H_0: p \geq 0.35$, versus the alternate $H_1: p \leq 0.15$, where p is probability of grade II_IV acute GVHD. These figures result in a two-stage design of 25 and 30 patients during stage 1 and 2 respectively, with an alpha of 0.05 and beta of 0.20. In the first stage, we will enter 25 patients undergoing matched sibling transplantation. If 6 or more of these patients develop grade II-IV acute GVHD, we will stop and conclude in favor of $H_0: p \geq 0.35$. If only 5 or less of the first 25 patients develop grade II-IV acute GVHD, we will enter an additional 5 patients, for a total of 30 patients. In the final analysis, if 7 or fewer of the 30 patients develop grade II-IV acute GVHD we will reject null hypothesis.

For the unrelated donor HCT arm of this study we will consider the “experimental” acute GVHD prophylactic regimen of atorvastatin/tacrolimus/methotrexate to be no more effective than GVHD prophylaxis with tacrolimus/methotrexate alone, if the true probability of developing grade II-IV acute GVHD is more than 55% (p0). We will also assume that the new prophylactic regimen is worthy of further study if the true probability of grade II-IV acute GVHD is equal or less than 40% (p1). In statistical terms, we are testing the null hypothesis $H_0: p \geq 0.55$, versus the alternate $H_1: p \leq 0.35$, where p is probability of grade II_IV acute GVHD. These figures result in a two-stage design of 30 and 39 patients during stage 1 and 2 respectively, with an alpha of 0.05 and beta of 0.20. In the first stage, we will enter 30 patients undergoing unrelated donor transplantation. If 14 or more of these patients develop grade II-IV acute GVHD, we will stop and conclude in favor of $H_0: p \geq 0.55$. If only 13 or less of the first 30 patients develop grade II-IV acute GVHD, we will enter an additional 9 patients, for a total of 39 patients. In the final analysis, if 17 or fewer of the 39 patients develop grade II-IV acute GVHD we will reject null hypothesis.

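### The final success cut-off is one event too lenient in both arms: 7/30 and 17/39 give a type I error of 0.069 and 0.079, not the stated 0.05

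*Combined protocol and SAP*

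**What the plan says.** Section 9 (Statistical Considerations) sets the primary decision rule for each arm. On the design it says "we will use an open-label, minimax two-stage design as specified by Simon".

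- **Sibling arm.** The null rate of grade II-IV acute GVHD is 35% and the alternative is 15%. The design is described as a "two-stage design of 25 and 30 patients during stage 1 and 2 respectively, with an alpha of 0.05 and beta of 0.20". At stage 1: "If 6 or more of these patients develop grade II-IV acute GVHD, we will stop". Otherwise: "If only 5 or less of the first 25 patients develop grade II-IV acute GVHD, we will enter an additional 5 patients", for 30 in total. At the end: "In the final analysis, if 7 or fewer of the 30 patients develop grade II-IV acute GVHD we will reject null hypothesis".
- **Unrelated-donor arm.** The null rate is 55%, and the formal alternative hypothesis is 35%. Alpha and beta are again 0.05 and 0.20. Thirty patients enter stage 1. The arm stops at 14 or more events; with 13 or fewer it adds 9 patients, for 39 in total. At the end: "In the final analysis, if 17 or fewer of the 39 patients develop grade II-IV acute GVHD we will reject null hypothesis".

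**The concern.** In a Simon design the stage sizes, the stage 1 limit, the final limit and the error rates are tied together. Once the first three are fixed, type I error and power follow by exact calculation. Here the stated alpha does not follow from the stated rules.

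This is the primary efficacy decision in both arms, and Section 9 plans to analyse the arms separately with separate publications in view. An arm that finishes at exactly 7/30 or 17/39 would be declared positive at a claimed 5% error rate that the rule does not meet. Those outcomes are realistic. The chance of finishing at exactly 7/30 is about 5% if the true rate is 20 to 25%. The chance of finishing at exactly 17/39 is about 7 to 8% if the true rate is 40 to 45%.

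**Working it through.** **Inputs (all from Section 9)**

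| | Sibling | Unrelated |
|---|---|---|
| Null rate p0 | 0.35 | 0.55 |
| Alternative p1 | 0.15 | 0.35 (formal hypothesis) |
| Stage 1 size n1 | 25 | 30 |
| Continue if events ≤ a1 | 5 | 13 |
| Total n | 30 | 39 |
| Reject H0 if events ≤ a | 7 | 17 |
| Stated alpha / beta | 0.05 / 0.20 | 0.05 / 0.20 |

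The second stage figure is the cumulative total, because the text adds 5 and 9 patients to reach 30 and 39. The accrual estimate of 55-69 agrees: 25 + 30 = 55 and 30 + 39 = 69.

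**Formula**

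P(reject | p) = Σ over x from 0 to a1 of Bin(x; n1, p) × P(X2 ≤ a − x), where X2 ~ Bin(n − n1, p). Evaluate at p0 for type I error and at p1 for power.

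**Step 1: sibling rule as written, at p = 0.35**

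| Stage 1 events x | P(x of 25) | P(X2 ≤ 7 − x), 5 patients | Product |
|---|---|---|---|
| 0 | 0.00002 | 1 | 0.00002 |
| 1 | 0.00028 | 1 | 0.00028 |
| 2 | 0.00183 | 1 | 0.00183 |
| 3 | 0.00755 | 0.99475 | 0.00751 |
| 4 | 0.02236 | 0.94598 | 0.02116 |
| 5 | 0.05058 | 0.76483 | 0.03868 |

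The sum is 0.0695. The stated 0.05 is not reproduced. With a final limit of 6, the last factor for x = 5 falls from 0.76483 to 0.42842 and for x = 4 from 0.94598 to 0.76483. The sum becomes 0.0480.

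**Step 2: the same calculation in both arms**

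| Rule | Type I error | Power at p1 |
|---|---|---|
| Sibling, ≤7 of 30 (plan) | 0.0695 | 0.834 |
| Sibling, ≤6 of 30 | 0.0480 | 0.807 |
| Unrelated, ≤17 of 39 (plan) | 0.0787 | 0.849 |
| Unrelated, ≤16 of 39 | 0.0499 | 0.806 |

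Relative to the claim: 0.0695 / 0.05 = 1.39 and 0.0787 / 0.05 = 1.57.

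**Step 3: what the minimax design should be**

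An exhaustive search took the smallest n with alpha ≤ 0.05 and power ≥ 0.80, then the smallest expected n under p0. From the plan's inputs it returns:

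- Sibling: 25 patients, continue at ≤5; 30 patients, reject at ≤6.
- Unrelated: 30 patients, continue at ≤13; 39 patients, reject at ≤16.

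Both stage sizes, both totals and both stage 1 limits match the plan. Only the final limit differs, by one event, in the same direction in each arm.

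**Step 4: other readings**

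None restores alpha 0.05 with the written cut-offs and adequate power.

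- No stage 1 stop: alpha 0.124 and 0.102.
- Second number read as additional patients (totals 55 and 69): alpha near 0, but power 0.40 and 0.04.
- Stage 1 limit one lower: sibling alpha 0.031 with power 0.68; unrelated alpha 0.054 with power 0.77.

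**Likely cause (inference)**

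Simon's design is usually written for successes. Counted as event-free patients, the same designs retain H0 at 23 or fewer of 30 and at 22 or fewer of 39. Subtracting gives 30 − 23 = 7 and 39 − 22 = 17, the plan's numbers. Those are the largest event-free counts that do *not* reject; rejection needs 24 or 23 event-free, that is 6 or 16 events.

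**The case against.** The arithmetic is not in dispute. The case on the other side concerns importance and completeness.

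- **The excess is small for a phase II screen.** It is 2.1 and 2.9 percentage points, and only a result of exactly 7/30 or 17/39 changes the conclusion. Uncertainty in the null rate matters at least as much. Section 9 gives 30-40% for siblings; at 30% the chance of a positive result is 0.135 even with the corrected rule (0.175 as written). For unrelated donors without ATG it gives 50-60%; at 50% the figures are 0.153 and 0.211. This is fair, but the plan states 0.05 and its rule does not meet it.
- **Ordinary confidence bounds do not separate the two rules.** The exact single-stage one-sided 95% upper bounds at 7/30 and 17/39 are 39.4% and 57.9%, above the nulls. But 6/30 and 16/39 give 35.7% and 55.4%, also above them. This stands, so the point should not rest on those bounds. Allowing for the two stages, the true rate at which each rule's rejection probability equals 0.05 is 36.6% and 56.9% for the written cut-offs, against 34.8% and 54.99% for the corrected ones. That comparison does separate them.
- **The unrelated alternative is 40% in the narrative but 35% in the hypothesis.** Type I error depends only on the null, so alpha is unaffected. Power does depend on it: at 40% it is 0.660 as written and 0.588 with the corrected cut-off. Only 35% reproduces 30/39; an alternative of 40% would need 70 patients.
- **A later paragraph of Section 9 conflicts with these rules.** It gives a maximum of 30 per arm and a stage 1 condition of 10 or fewer events. It sets no final success rule, so this is a separate inconsistency.

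**Conclusion.** The final decision rule is wrong as written in both arms. The stated alpha of 0.05 is 0.0695 for siblings and 0.0787 for unrelated donors. The stage sizes and stage 1 limits are correct for the stated design; only the final cut-off is off, by one event in each arm. Power is not harmed by the error: the written rules exceed 80% at 15% and 35%.

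The result assumes nulls of 35% and 55%, a binary day +100 outcome known for every counted patient, and stopping exactly as described. It does not model the replacement of patients who die of relapse within 100 days. The corrected unrelated rule sits at 0.0499, so it has almost no margin if the counted set departs from those assumptions.

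**What to change.** In Section 9, change the final rules to 6 or fewer of 30 (sibling) and 16 or fewer of 39 (unrelated). Sample sizes and stage 1 rules in those paragraphs stay as they are. Type I error becomes 0.0480 and 0.0499. Power falls by 2.7 points to 0.807 (at 15%) and by 4.3 points to 0.806 (at 35%), still above the stated 80%.

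If the sponsor prefers 7 and 17, state alpha as 0.07 and 0.08 instead.

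Either way, the change costs two numbers and no patients. Make it before the final counts are known, because a success threshold altered afterwards would not be credible. In the same amendment, reconcile the 40% and 35% alternatives for the unrelated arm, since the power figure holds only at 35%. Also reconcile the sentence giving a maximum of 30 per arm and 10 or fewer stage 1 events with the arm-specific rules.

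### The unrelated-donor arm is given two target GVHD rates, 40% and 35%; the 30/39 design has its stated 80% power at 35% but only 59–66% at 40%

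*Combined protocol and SAP*

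**What the plan says.** Section 9 (Statistical Considerations) announces that "we will use an open-label, minimax two-stage design as specified by Simon". For the unrelated-donor arm it then gives, in consecutive sentences:

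- **Null rate:** no better than tacrolimus/methotrexate alone "if the true probability of developing grade II-IV acute GVHD is more than 55% (p0").
- **Target rate in prose:** the regimen is worth pursuing "if the true probability of grade II-IV acute GVHD is equal or less than 40% (p1").
- **Formal hypotheses:** "testing the null hypothesis $H_0: p \geq 0.55$, versus the alternate $H_1: p \leq 0.35".
- **Design attributed to these figures:** "two-stage design of 30 and 39 patients during stage 1 and 2 respectively, with an alpha of 0.05 and beta of 0.20".
- **Stage 1:** "If 14 or more of these patients develop grade II-IV acute GVHD, we will stop and conclude in favor of $H_0: p \geq 0.55". Otherwise 9 more patients are entered, so 39 is the total and not the size of stage 2.
- **Final analysis:** the null is rejected with 17 or fewer cases among the 39.

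The sibling arm, described in the same section, uses one target (15%) in both the prose and the formal alternative. The mismatch is confined to the unrelated arm, and nothing else in the document says which value is meant.

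**The concern.** The target rate fixes the sample size and gives the stated power its meaning. Here it has two values for one arm, and the plan claims a single design with beta 0.20 follows from them. A two-stage design sized for a fall from 55% to 35% cannot have the same power for a fall from 55% to 40%.

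The ambiguity affects how the primary result is read. If the true rate is between 35% and 40%, the regimen is worth pursuing by one sentence and outside the alternative by the next. After a negative result, the 40% sentence together with beta 0.20 would suggest that a 40% rate had been given an 80% chance of detection. Choosing between the two targets once the data are known would be a post hoc decision.

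**Working it through.** **Inputs (all from Section 9, unrelated-donor arm).** Null rate 0.55; target 0.40 (prose) or 0.35 (formal alternative); alpha 0.05, one-sided from the form of the hypotheses; power 0.80; n1 = 30, n = 39; continue if 13 or fewer of 30 have grade II–IV GVHD; reject the null if 17 or fewer of 39 do.

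**Formula.** With X1 ~ Bin(30, p) and X2 ~ Bin(9, p), and final cut-off c,

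P(reject | p) = sum over x = 0..13 of P(X1 = x) × P(X2 ≤ c − x).

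**Step 1: reproduce the plan's design.** An exhaustive minimax search was run on the GVHD-free scale, where the null is 1 − 0.55 = 0.45 and the target is 1 − 0.35 = 0.65. It returns n1 = 30 and n = 39: stop with 16 or fewer GVHD-free of 30, and fail to reject with 22 or fewer GVHD-free of 39. In GVHD counts:

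- continue with at most 30 − 17 = 13 cases;
- reject with at most 39 − 23 = 16 cases.

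Exact alpha is 0.0499 and power at 35% is 0.806. The sample sizes, the stage 1 boundary and beta therefore all reproduce at 35%. The written final cut-off of 17 does not match: it is one higher than the minimax boundary and gives exact alpha 0.079. That is a separate error, so power is shown below for both cut-offs.

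**Step 2: power of the 30/39 design at each stated target.**

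| True rate | Reject if ≤17 of 39 (as written) | Reject if ≤16 of 39 (holds alpha) |
|---|---|---|
| 0.55 (type I error) | 0.0787 | 0.0499 |
| 0.40 | 0.6596 | 0.5878 |
| 0.35 | 0.8491 | 0.8058 |

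At 40%, beta is 1 − 0.6596 = 0.340 as written, or 1 − 0.5878 = 0.412 with the lower cut-off, against the stated 0.20.

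**Step 3: stage 1 alone.** At 40%, P(X1 ≤ 13) = 0.7145, so the arm stops at stage 1 with probability 1 − 0.7145 = 0.2855. Power cannot exceed the probability of passing stage 1. With this stage 1 rule, no final cut-off could give 80% power at 40%.

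**Step 4: what a 40% target would need.** The same search with null 0.45 and target 0.60 on the GVHD-free scale gives n1 = 42 (continue with 22 or fewer cases) and n = 70 (reject with 31 or fewer cases), with alpha 0.046 and power 0.800.

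**The case against.** The strongest reply is that this is one uncorrected number in a prose sentence. The formal alternative, both sample sizes, the stage 1 boundary and beta all fit 35%, and no decision rule uses the 40% figure. Correcting it would change no patient's path through the trial. On that reading the stated power is met (0.806 or 0.849), and the shortfall is hypothetical. This is probably how the text arose, and the power loss does depend on 40% being the real target.

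It does not dispose of the point, because 40% is a plausible target on the plan's own figures. Section 9 puts RIC unrelated-donor GVHD at 45–55% with ATG and 50–60% without, and Section 1.7 says the aim is to see whether atorvastatin can hold the rates seen with ATG. A true rate of 40% lies below the whole ATG range and would meet that aim. A reader cannot dismiss it as an obvious slip.

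Three narrower objections are fair:

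- Of the 59–66% range, only 66% belongs to the rule as written; 59% assumes the final cut-off is also corrected.
- The plan does not state that a negative result means the regimen should be dropped; that is an inference from how such designs are used.
- The plan also intends a retrospective comparison with ATG-treated patients, so the two-stage test is not the only evidence for this arm.

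None of these removes the contradiction.

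**Conclusion.** The plan is wrong as written: one arm has two target rates, and only 35% gives the stated 30/39 design with at least 80% power. At a true rate of 40% the regimen would fail the test about 34% of the time under the written rule, or 41% with the cut-off that holds alpha, instead of 20%. Stage 1 stopping accounts for 29 percentage points of either figure.

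These results assume independent patients with a common GVHD probability, every patient evaluable at day +100, and the two-stage rule followed exactly. The comparison is between the two stated targets; power is higher still for true rates below 35%. If 35% was always intended, the harm is a misstated target and not an underpowered arm, but the plan must still state a single value.

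**What to change.** State one target for the unrelated-donor arm in Section 9.

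- **If 35% is intended** (the value that fits the design): change the 40% in the prose sentence to 35%. This costs one number and no patients.
- **If 40% is intended:** keep 39 patients and replace the beta 0.20 statement with the actual power at 40%, about 59% with a final cut-off of 16 or fewer (66% if the written 17 is kept, but then alpha is 0.079). This costs a less favourable power statement and no patients.
- **If 40% is intended and 80% power is required:** resize the arm to 42 in stage 1 and 70 in total. That adds 70 − 39 = 31 patients, and this arm alone would exceed the 55–69 accrual estimate for the whole study.

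The choice should be made without reference to outcome data. The final cut-off needs its own correction whichever target is chosen, since changing the target does not repair it.
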